| $AUC_{0 \rightarrow t}$ | The AUC from time zero (= dosing time) to the last sampling time (t_{last}) at which the concentration is at or above the lower limit of quantification |
| $AUC_{extra\%}$ | The AUC from time t_{last} extrapolated to infinity given as percentage of $AUC_{0 \rightarrow \infty}$ |
| BE | Bioequivalence |
| BMI | Body Mass Index |
| CI | Confidence Interval |
| CL/f | The apparent total body clearance of drug following extravascular administration. |
| C_{max} | Maximum observed plasma concentration |
| CRO | Contract Research Organization |
| CSR | Clinical Study Report |
| CTR | Clinical Trial Report |
| CTMS | Clinical Trial Management System |
| CTP | Clinical Trial Protocol |
| CV | Coefficient of Variation (%) |
| ECG | Electrocardiogram |
| ECOG | Eastern Cooperative Oncology Group |
| eCRF | Electronic Case Report Form |
| GCP | Good Clinical Practice |
| GeoCV% | Geometric Coefficient of Variation |
| GeoMean | Geometric Mean |
| GIR | Glucophage Immediate Release |
| HR | Hazard ratio |
| HAV | Hepatitis A Virus |
| HbA _{1C} | Glycosylated Hemoglobin Type A _{1C} |

| | |
|------------|--|
| HBsAg | Hepatitis B Surface Antigen |
| HCV | Hepatitis C Virus |
| HIV | Human Immunodeficiency Virus |
| ICF | Informed Consent Form |
| ICH | International Conference on Harmonization |
| IMP | Investigational Medicinal Product |
| LLOQ | Lower Level of Quantification |
| Max | Maximum |
| Mean | Arithmetic mean |
| Min | Minimum |
| MedDRA | Medical Dictionary For Regulatory Activities |
| MRI | Magnetic Resonance Imaging |
| MSS | Merck Santé s.a.s. in Semoy |
| N | Number of non-missing observations |
| PK | Pharmacokinetics |
| PR | Partial Response |
| PT | Preferred team |
| SAE | Serious Adverse Event |
| SASS | Sino-American Shanghai Squibb Pharmaceuticals Ltd |
| SAP | Statistical Analysis Plan |
| SBP | Systolic Blood Pressure |
| SD | Standard Deviation |
| SDTM | Study Data Tabulation Model |
| SEM | Standard Error of the Mean |
| SOC | System Organ Class |
| $t_{1/2}$ | Apparent terminal half-life |
| T2DM | Type 2 Diabetes Mellitus |
| TEAE | Treatment-Emergent Adverse Event |
| t_{last} | The last sampling time at which the concentration is at or above the lower limit of quantification |
| t_{max} | The time to reach the maximum observed concentration |
| TP | Treponema Pallidum |

| | |
|-------------|--|
| $V_{z/f}$ | Apparent volume of distribution during the terminal phase following extravascular administration |
| λ_z | Terminal elimination rate constant |

4 Modification History

| Unique Identifier for SAP Version | Date of SAP Version | Author | Changes from the Previous Version |
|-----------------------------------|---------------------|--------|-----------------------------------|
| Draft V0.1 | 17 November 2017 | PPD | Not Applicable –First Version |
| Draft V0.2 | 01 December 2017 | PPD | Updated based on SBR comments |
| Draft V0.3 | 20 December 2017 | PPD | Updated based on Sponsor comments |
| Draft V0.4 | 12 January 2018 | PPD | Updated based on Sponsor comments |
| Draft V0.5 | 15 January 2018 | PPD | Updated based on Sponsor comments |
| Draft V0.6 | 22 January 2018 | PPD | Updated based on Sponsor comments |

5 Purpose of the Statistical Analysis Plan

The purpose of this Statistical Analysis Plan (SAP) is to document technical and detailed specifications for the final analysis of data collected for protocol MS200084_0009, version 2.0. Results of the analyses described in this SAP will be included in the Clinical Study Report (CSR). Additionally, the planned analyses identified in this SAP will be included in regulatory submissions or future manuscripts. Any post-hoc, or unplanned analyses performed to provide results for inclusion in the CSR but not identified in this prospective SAP will be clearly identified in the CSR.

The SAP is based upon Section 8 (Statistics) of the trial protocol and protocol amendments and is prepared in compliance with ICH E9.

6 Summary of Clinical Trial Features

| | |
|-------------------------|--|
| Trial Objectives | 
Primary Objective:
 
 To assess bioequivalence (BE) between the GIR formulation manufactured in China (test investigational medicinal product [IMP]) and that manufactured in France (reference IMP) following single oral dose administrations under fasting and fed conditions. 
Secondary Objectives:
 
 To compare additional pharmacokinetic (PK) parameters of GIR after single dose administrations of test and reference products. To examine the safety and tolerability of GIR after single dose administrations of test and reference products. |
|-------------------------|--|

| | |
|------------------------|--|
| Trial Endpoints | 
Primary Endpoints:
 
• Primary Endpoints will be the PK parameters area under the (plasma) concentration-time curve from time 0 (dosing time) to the last sampling time (t_{last}) at which the concentration is at or above the lower limit of quantification (LLOQ) ($AUC_{0 \rightarrow t}$) and maximum plasma concentration observed (C_{max}) of metformin, the active ingredient of GIR tablet. 
Secondary Endpoints:
 
• Pharmacokinetic endpoints: include time of maximum plasma concentration observed (t_{max}), half-life ($t_{1/2}$), area under the plasma concentration curve from time 0 to infinity ($AUC_{0 \rightarrow \infty}$), the extrapolated part of area under the plasma concentration-time curve ($AUC_{extra\%}$), terminal elimination rate constant (λ_z), total clearance following extravascular administration (CL_f), and apparent volume of distribution during the terminal phase following extravascular administration ($V_{z/f}$) for metformin, as well as safety and tolerability.• Safety Endpoints: include adverse events, vital signs (blood pressure, pulse rate, temperature and respiration), laboratory tests (biochemistry, hematology, and urinalysis), electrocardiogram (ECG), physical examination, and concomitant medications. |
|------------------------|--|

| | |
|--|---|
| 
Trial Design
 | 
This trial is designed as a Phase I, open-label, randomized, 2-period, 2-sequence, crossover trial to assess BE between single oral doses of GIR from different manufacturing facilities, each given concomitantly as a single dose in fasting or fed state. Subjects will be randomized to receive, in each period, either:
 
 • 1 tablet of 500 mg GIR (manufactured in Sino-American Shanghai Squibb Pharmaceuticals Ltd. [SASS]/China) or • 1 tablet of 500 mg GIR (manufactured in Merck Santé in Semoy [MSS]/ France). • Drug administration will be done with or without food depending on group allocation to either fed or fasted condition. 
The trial has a duration of approximately 4 weeks including:
 
 • A screening period within 2 weeks before the first GIR administration • First dosing/sampling period up to 2 days (48 hours) after dosing • A wash-out period of approximately 7 days after the first GIR administration • Second dosing/sampling period up to 2 days (48 hours) after dosing 
A conditional follow-up examination period (only for subjects who has AE during the trial and ongoing at discharge) up to 7 days following the last IMP administration.
 |
| 
Planned number of subjects
 | 
A total of 44 healthy male and female Chinese subjects will be enrolled in the trial, with each gender representing no less than 1/4 of the total number (also evenly allocated to fasting vs. fed group), and are statistically powered to provide adequate sample size for BE testing.
 |
| 
Treatment and Trial Duration
 | 
The trial has a duration for each subject of approximately 4 weeks, including:
 
 • A screening period within 2 weeks before the first IMP administration • First dosing/sampling period up to 2 days (48 hours) after dosing • A washout period of at least 7 days after the first IMP administration • Second dosing/sampling period up to 2 days (48 hours) after dosing • A conditional follow-up examination period (only for subjects who has AE during the trial and ongoing at discharge) up to 7 days following the last IMP administration. |

| | |
|-----------------------------------|--|
| | 14 days prior to the first IMP administration on Day 1) followed by 2 |
| Pharmacokinetics | The plasma concentrations of metformin will be determined by a validated LC/MS analytical method. Pharmacokinetic parameters (Primary and Secondary Endpoints) will be calculated according to non-compartmental analysis methods. The mixed trapezoidal rule will be used to calculate the area under the plasma concentration curve. |
| Randomization and Blinding | A total of 44 eligible healthy male and female Chinese subjects (26 in fasting state and 18 in fed state) who meet the eligibility criteria will be randomized (with each gender representing no less than 1/4 of the total number within each group) on Day 1, in a 1:1 ratio to 1 of 2 treatment sequences: Sequence A-B or Sequence B-A. As this is an open-label trial, no method of blinding was used. |

7 Sample Size/Randomization

7.1 Sample Size

The BE is declared if all comparisons in primary hypothesis achieve the criteria - the 90% confidence intervals (CI) for the ratios between test and reference of geometric means of both $AUC_{0 \rightarrow t}$ and C_{max} for metformin in plasma are within 80.00% to 125.00% in both the fasted and fed group.

Based on the results of previously conducted BE trial PK data, (Iran BE 2013 [fasted] and EML056023-H105 [fed]) [1,2], Glucophage/metformin IR formulation has shown relatively low intra-individual Coefficient of Variation (CV), as shown below (Table and Table).

IRAN BE-2013

- Test: Single dose of metformin IR 500 mg tablets manufactured by PPD (Iran) under fast condition
- Reference: Single dose of metformin IR 500 mg tablets manufactured by Merck (Darmstadt) under fast condition

Table 1 Results from IRAN Bioequivalence Study-2013 Fasting (n= 21)

| Parameter | Intra-Subject CV (%) | Geometric Mean | | Ratio ^a (%) | 90% Confidence Limits ^a (%) | |
|-------------------------|----------------------|----------------|-----------|------------------------|--|--------|
| | | Test | Reference | | Lower | Upper |
| C_{max} | 17.5 | 1404.5 | 1425.5 | 102 | 92.14 | 110.95 |
| $AUC_{0 \rightarrow t}$ | 13.8 | 7946.5 | 8049.5 | 100 | 92.72 | 107.37 |

$AUC_{0 \rightarrow t}$ = area under the plasma concentration-time curve from time 0 to time t; C_{max} = the maximum plasma concentration observed; CV= Coefficient of Variation

^a Results from ANOVA Model

CCI

As shown in Table and Table , if applying these CVs together with applicable BE criteria for AUC_{0-t} and C_{max} [0.80 – 1.25], and CCI

In total, 44 subjects should be included in the trial.

Table 3 Sample size and power – Assuming Coefficient of Variation = 17.5% for C_{max} and 13.8% for AUC_{0-t} (Iran BE 2013 Fasting) and assume 5% variation for all ratios (95% to 105%)

| Fasted Condition | | | |
|------------------|-------------|-------------|------------------|
| Sample Size | Power (%) | | |
| | C_{max} | AUC_{0-t} | Joint Power |
| 18 | 88.2 | 97.4 | > 85.9 |
| 20 | 91.3 | 98.4 | > 89.9 |
| 22 | 93.6 | 99.0 | > 92.7 |

AUC_{0-t} = area under the plasma concentration-time curve from time 0 to time t; C_{max} = the maximum plasma concentration observed

CCI

CCI

7.2 Randomization

Each eligible subject will be allocated to a treatment sequence according to a computer-generated randomization schedule. Subjects will be identified only by their assigned subject number. The subjects will receive consecutive subject numbers in the order of their enrollment into the trial.

A total of 44 eligible healthy male and female Chinese subjects (26 in fasting state and 18 in fed state, Table) who meet the eligibility criteria will be randomized (with each gender representing no less than 1/4 of the total number within each group) on Day 1, in a 1:1 ratio to 1 of 2 treatment sequences: Sequence A-B or Sequence B-A as presented in Table .

In sequence A-B, subjects will receive test GIR tablets (Treatment A) in Period 1 and reference GIR tablets (Treatment B) in Period 2. In sequence B-A, subjects will receive reference GIR tablets in Period 1 and test GIR tablets in Period 2 after Washout.

Table 5 Randomization Allocation

| | Day 1 of Period 1 | Day 1 of Period 2 |
|-----------------------|---------------------|---------------------|
| Fasting group (n= 26) | Treatment A (n= 13) | Treatment B (n= 13) |
| | Treatment B (n= 13) | Treatment A (n= 13) |
| Fed group (n= 18) | Treatment A (n= 9) | Treatment B (n= 9) |
| | Treatment B (n= 9) | Treatment A (n= 9) |

Subjects will only be replaced if the number of subjects within each group falls below 20 (fasting) or 12 (fed). The subject who is replacing a discontinued subject will then be allocated to the treatment sequence of the subject who discontinued.

8 Overview of Planned Analyses

The methods described in this document will be applied to the preparation of tables, figures and listings (TLFs). Statistical analyses will be performed using cleaned electronic clinical report form (eCRF) data collected.

This SAP will cover the final analysis only. The final analysis will be performed only after the last subject has completed the study with all study data in-house and all data queries resolved. The SAP will be finalized prior to database lock.

9 Changes to the Planned Analyses in the Clinical Trial Protocol

The Screening Population has been added to include all subjects who signed informed consent in the study.

10 Protocol Deviations and Analysis Sets

10.1 Definition of Protocol Deviations

Protocol deviations describe how close the study has been conducted according to the protocol as expected per GCP. Some of these deviations may be significant contributors to analysis bias.

Important protocol deviations are protocol deviations that might significantly affect the completeness, accuracy, and/or reliability of the study data or that might significantly affect a subject's rights, safety, or well-being.

Examples of clinically important protocol deviations or important events for PK include, but may not be limited to, the following:

- Subjects that are dosed on the study despite not satisfying the inclusion criteria
- Subjects that develop withdrawal criteria whilst on the study but are not withdrawn
- Subjects that receive the wrong treatment or an incorrect dose
- Subjects that receive an excluded concomitant medication
- Vomiting following oral dosing (handling of this event is described under Section 10.2; each instance will be discussed in the CSR)
- Deviation from GCP
- Sample processing errors that may lead to inaccurate bioanalytical results
- Failure to fast (in fasted arm) or incomplete meal consumption (in fed arm) prior to dosing

The following deviations will be identified and confirmed prior to or at the Data Review Meeting at the latest. Important protocol deviations include:

- Deviations from the inclusion and exclusion criteria
- Deviations post inclusion

A data review meeting will be held to discuss and update the definition of important protocol deviations so as to determine the evaluability of the subjects prior to database lock.

10.2 Definition of Analysis Sets and Subgroups

Screening Population

The Screening population includes all subjects who have signed the main informed consent (i.e., screening failures plus subjects enrolled).

Safety Population

The Safety Population includes all subjects who received at least 1 dose of IMP. In general, clinical data will be analyzed for the Safety Population.

Pharmacokinetic Population

The PK Analysis Set includes all subjects who completed the trial with adequate trial medication compliance, without any relevant protocol violations or events with respect to factors likely to affect the comparability of PK results, and with sufficient evaluable data to determine primary endpoints ($AUC_{0 \rightarrow t}$ and C_{max}) for both treatments. If subjects receive concomitant medication that potentially affects PK for the treatment of an AE, their inclusion in the PK Analysis Set will be decided on a case-by-case basis. Emesis occurring within two times of the median t_{max} for a given treatment will be considered a relevant event likely to affect the comparability of PK results. Similarly, a predose concentration for a given treatment period which exceeds 5% of C_{max} will be considered a relevant event affecting PK results. All PK analyses will be based on the PK Analysis Set. Data for subjects excluded from the PK Analysis set will be included in listings.

11 General Specifications for Statistical Analyses

Output Presentations:

The shells provided with this SAP describe presentations for this study and therefore the format and content of the summary tables, listings and figures to be provided by IQVIA Biostatistics. Unless otherwise indicated all analyses will be presented separately for the two treatments (Treatment A and Treatment B) and for two treatment sequences (Sequence A-B and Sequence B-A) under different food condition (fed and fasted).

Listings

All listings will be reported separately by food condition and sorted by treatment or treatment sequence (A-B or B-A), and/or scheduled time point, as appropriate. Data which are only collected before administration of trial drug and/or at end of study will be sorted by subject and scheduled time point (if appropriate).

All PK concentrations will be reported and analyzed with the same precision as the source data provided by the bioanalytical laboratory or clinical laboratory regardless of how many significant figures or decimal places the data carry. In export datasets, as well as in the Study Data Tabulation Model (SDTM) PP/XD domain, PK parameters will be provided with full precision, and will not be rounded.

Pharmacokinetic parameters and actual elapsed sample collection times will be rounded for reporting purposes in by-subject listings. Actual elapsed sample collection times will be rounded to two decimal places with units of hours. For PK parameters, the standard rounding procedure will be as follows:

- Parameters directly derived from source data (e.g., C_{max}) will be reported and analysed with the same precision as the source data.
- Parameters derived from actual elapsed sample collection times (e.g., t_{max}) will be reported to two decimal places with units of hours.

- Values of AUC will be rounded to 3 significant figures.
- Percentages not derived directly from source data (e.g., AUC_{extra%}) will be reported to 3 significant figures.
- Other parameters (e.g., $t_{1/2}$, λ_Z , CL_f, V_{z/f}) will be reported with 3 significant figures.

Tables and Descriptive Statistics

All data will be summarized by food condition, treatment or treatment sequence, and/or scheduled time point, as appropriate. Repeated and unscheduled measurements included in the listings will not be used for statistical analyses or summaries, unless the repeated measurement was performed due to unreliable values/technical reasons, e.g., clotted samples. Unscheduled measurements will not be included in by-visit table summaries and graphs, but will contribute to the baseline value and best/ worst case value where required.

Metformin concentration in plasma and its PK parameters will be presented in tables and descriptively summarized by food condition, treatment, and/or nominal time point, as appropriate.

Presentation of PK Concentration Data

Pharmacokinetic concentration data will be descriptively summarized using: number of non-missing observations (N), arithmetic mean (Mean), standard deviation (SD), standard error of the mean (SEM), CV%, minimum (Min), median (Median) and maximum (Max).

Descriptive statistics of PK concentration data will be calculated using values with the same precision as the source data, and rounded for reporting purposes only. The following conventions will be applied when reporting descriptive statistics of PK concentration data:

| | |
|-------------------------|----------------------|
| Mean, Min, Median, Max: | 3 significant digits |
| SD: | 4 significant digits |
| CV%: | 1 decimal place |

Descriptive statistics of plasma concentrations below the LLOQ will be taken as zero.

Presentation of PK Parameter Data

Pharmacokinetic parameter data will be descriptively summarized using: N, Mean, SD, CV%, Min, Median, Max, geometric mean (GeoMean), the geometric coefficient of variation (GeoCV%), and the 95% CI for the GeoMean (LCI 95% GM, UCI 95% GM).

Descriptive statistics of PK parameter data will be calculated using full precision values, and rounded for reporting purposes only.

The following conventions will be applied when reporting descriptive statistics of PK parameter data:

| | |
|--|----------------------|
| Mean, Min, Median, Max, GeoMean, 95% CI: | 3 significant digits |
|--|----------------------|

| | |
|----------------|----------------------|
| GeoMean ratio: | 2 decimal places |
| SD: | 4 significant digits |
| CV%, GeoCV%: | 1 decimal place |

Presentation of continuous and qualitative variables

Continuous variables will be summarized using the following descriptive statistics unless otherwise specified, i.e.,

- Number of subjects (N), number of subjects with non-missing values
- Mean, SD
- Median
- Minimum and maximum

Qualitative variables will be summarized by counts and percentages.

Unless otherwise stated, the calculation of proportions will be based on the number of subjects of the analysis set of interest. Therefore, counts of missing observations will be included in the denominator and presented as a separate category.

In case the analysis refers only to certain visits, percentages will be based on the number of subjects still present in the trial at that visit, unless otherwise specified.

Software:

Pharmacokinetic parameters will be derived using noncompartmental methods with the validated computer program Phoenix[®] WinNonlin[®] 6.4 or higher (PPD [REDACTED]). Pharmacokinetic figures will be developed using SigmaPlot[®] 12.5 or higher (PPD [REDACTED]), Phoenix[®] WinNonlin[®] 6.4 or higher, or SAS[®] Windows Version 9.4 or higher (PPD [REDACTED]).

All other statistical analyses will be conducted using SAS[®] Version 9.4 or higher.

Definition of baseline:

Unless otherwise specified, baseline for end of study is defined as the last non-missing measurement taken prior to or on the day of the first IMP administration (including unscheduled assessments as applicable).

For vital signs, the assessment performed within 4 hours prior to IMP administration in each treatment period will be considered as baseline for the treatment period. If there is no time point, the last non-missing assessment prior to dosing in each period will be taken as baseline.

In the case where the last non-missing measurement and the dosing date/time coincide, that measurement will be considered baseline, but medications commencing on the first IMP administration date will be considered post-baseline.

Definition of End of Study

Unless otherwise specified, end of study is defined as the last measurement taken prior to or on the day of discharge (D10 or any special day for Premature Withdrawal Visit).

Definition of duration:

Duration will be calculated by the difference of start and stop date + 1 (e.g. survival time (days) = date of death – date of randomization + 1) (if not otherwise specified).

Conversion factors:

The following conversion factors will be used to convert days into months or years:

1 month = 30.4375 days

1 year = 365.25 days.

Common calculations:

For quantitative measurements, change from baseline will be calculated as:

Test Value at Visit X – Baseline Value

Handling of discontinued subjects and missing data:

Unless otherwise specified, data from discontinued subjects will not be replaced. Handling of missing data for PK parameter calculations are discussed under Section 16.3.2.

In all subject data listings, imputed values will be presented. In all listings imputed information will be flagged.

Missing statistics, e.g. when they cannot be calculated, should be presented as “nd”. For example, if $n=1$, the measure of variability (SD) cannot be computed and should be presented as “nd”. If $n=2$, summaries will not be computed and will be presented as “nd”.

For the derivation of new date variables the following rules will apply:

Partial birth dates will be handled this way: day will be imputed as 15 if it is missing, and month imputed as June if missing. If both of day and month are missing, they will be imputed as July 1st. If year is missing then the date will not be imputed.

Any adverse event (AE) with incomplete start/time and or end dates will be handled as described below for the classification as treatment-emergent, assignment to treatment periods, and calculation of duration.

- AE with unknown start time but known start date, will be imputed with a time of 00:00 hours, unless the start date corresponds to any given dosing date, in which case time of dosing will be used instead. However, if this results in a start time after end time of the AE, then the start time will be imputed to 00:00 hours instead.
- Any AE with completely unknown start date will be imputed with date and time of the first IMP administration, unless the end date (imputed if needed) is known and prior to first IMP administration. In the latter case, the start date will be missing.
- AE with partially missing start date but in the same year (when day and month are missing) or in the same month and year (if the day is missing) as first IMP administration then the start date will be replaced by the minimum between first IMP administration and AE resolution date. In all other cases the missing onset day or onset month will be replaced by 01.
- Adverse event with completely unknown end date will be imputed with the date of study completion (or in case of withdrawal, date of discontinuation).

Partially known end dates will be treated as follows:

- If only the day is missing, the last day of the month will be imputed or the date of study completion/discontinuation if earlier.
- If day and month are both missing, then the end date of 31 December will be imputed or the date of study completion/discontinuation if earlier.

Assignment to the different treatment periods will be performed after the imputations have been performed. An AE will be assigned to a specific treatment period if it occurs on or after the IMP administration scheduled for that period and before the IMP administration in the next period (or study completion for the last period).

Trial day:

Trial day will be calculated from the reference start date, and will be used to show start/end day of assessments and events. Reference start date is defined as the day of the first IMP administration in period 1. Trial Day 1 is the day of first IMP administration in period 1. The day before is defined as Trial Day -1 (no Trial Day 0 is defined). Trial day will be calculated accordingly:

- If the date of the event is on or after the reference start date then:

$$\text{Trial day} = (\text{date of event} - \text{reference start date}) + 1.$$

- If the date of the event is prior to the reference start date then:

$$\text{Trial day} = (\text{date of event} - \text{reference start date}).$$

In the situation where the event date is partial or missing, the date will appear partial or missing in the listings, and Trial Day and any corresponding durations will be presented as missing. Rules of handling missing dates relevant to efficacy will be specified in the subsequent sections.

12 Trial Subjects

This section includes specifications for reporting subject disposition and treatment/trial discontinuations. Additionally, procedures for reporting protocol deviations are provided.

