5.5.2 Withdrawal from the Trial

Subjects are free to discontinue the trial at any time without giving their reasons. A subject must be withdrawn in the event of withdrawal of the subject's consent. Furthermore, participation in this clinical trial can be discontinued by the Investigator for one of the following reasons:

- 1. Adverse events(AEs), as assessed by the Investigator to affect the subject safety or the outcome of the trial endpoints
- 2. Significant protocol violation such as noncompliance with restrictions regarding alcohol and drug use, and nonadherence to the fasting or fed conditions
- 3. Difficulties with blood collection
- 4. Emesis experienced within 4 hours following drug administration because of possibly incomplete absorption (this period of time corresponds also to 2 times the median time of maximum plasma concentration [t_{max}] of GIR). Subjects experiencing vomiting later than 4 hours postdose will not be withdrawn unless otherwise decided by the Investigator in light of subject's safety or trial integrity
- 5. Subject is uncooperative during the trial
- 6. Use of any ongoing or concomitant medication that is prohibited

Concomitant medication of any drug except pain relief medication (paracetamol) is prohibited, the administration of paracetamol should not exceed 1 g per day and not more than 3 consecutive days. Details of reasons for premature withdrawal of subjects will be recorded and documented in the final report.

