8.4 Analysis Sets

Safety Population

The Safety Population includes all subjects who received at least 1 dose of IMP. In general, clinical data will be analyzed for the Safety Population.

Pharmacokinetic Population

The PK parameters will be analyzed based on PK population. The PK population may include all subjects who completed the trial with adequate trial medication compliance, without any relevant protocol deviations with respect to factors likely to affect the comparability of PK results, and with sufficient evaluable data to determine Primary Endpoints (AUC_{0-t} and C_{max}) for both treatments in both groups. If subjects would receive concomitant medication for the treatment of an AE, their inclusion in the PK population will be decided on case-by-case basis.

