16.2 Secondary Endpoint Analyses

All secondary PK endpoints will be descriptively summarized as described in Section 11. The secondary PK endpoints are the following parameters in plasma for metformin:

t_{\max} , $t_{1/2}$, λ_Z , $AUC_{0 \rightarrow \infty}$, $AUC_{\text{extra}\%}$, CL/f , $V_{z/f}$.

For t_{\max} , the Hodges-Lehmann estimates for the treatment differences and corresponding 90% CIs according to the Tukey method will be calculated.

The mixed-effects model for treatment comparison as described for the primary endpoints will also be applied to $AUC_{0 \rightarrow \infty}$. The ratios of geometric means and corresponding 90% CIs for Treatment A/Treatment B will be estimated separately for fed and fasted treatments. Graphs of individual $AUC_{0 \rightarrow \infty}$ values and geometric mean will be presented by treatment and food condition.

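### Does SAP 10.2 leave the emesis window for the PK Analysis Set undefined and at odds with the protocol's 4-hour rule?

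*SAP*

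**What the plan says.** Protocol 5.5.2 lists reasons for which the investigator may end a subject's participation. One is "Emesis experienced within 4 hours following drug administration because of possibly incomplete absorption", and the protocol adds that "this period of time corresponds also to 2 times the median time of maximum plasma concentration" of GIR. After that point the default reverses: "Subjects experiencing vomiting later than 4 hours postdose will not be withdrawn unless otherwise decided by the Investigator" on grounds of safety or trial integrity. One figure serves both products and both food conditions.

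Protocol 8.4 defines the PK population without naming emesis. It asks for subjects "without any relevant protocol deviations with respect to factors likely to affect the comparability of PK results", and Protocol 8.5.1 leaves analysis details to the SAP.

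SAP 10.2 repeats the comparability condition, adds events to deviations, and names two such events. One is "Emesis occurring within two times of the median" tmax for the treatment in question. The other is a predose concentration above 5% of Cmax. SAP 10.1 lists vomiting among the examples of important deviations or events, with the note "handling of this event is described under Section 10.2; each instance will be discussed in the CSR". It also counts subjects who meet a withdrawal criterion but are not withdrawn, and it provides for a data review meeting before database lock to settle evaluability. SAP Section 9 records one change from the protocol: "The Screening Population has been added to include all subjects who signed informed consent in the study".

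**The concern.** The SAP turns a stated number of hours into a multiple of a median that it does not identify. The median could be a prior value or this trial's own. It could be one figure or one per product, per food condition, or both. SAP Section 11 calls test and reference the two treatments, so a product-specific median is a natural literal reading.

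On that reading, and with the trial's own data, three things could follow. A subject who vomits after 4 h might stay in the trial under the protocol default and still be dropped from the primary analysis set. The same emesis time might exclude a subject after one product but not after the other. And membership would depend on tmax, which is itself a secondary endpoint: under SAP 16.2 "the Hodges-Lehmann estimates for the treatment differences and corresponding 90% CIs according to the Tukey method will be calculated" for it. SAP 16.3.1 runs all PK summaries on the PK Analysis Set, so the rule might also look circular. At stake is who enters the primary test in an open-label trial with minimum evaluable groups of 20 and 12.

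**Working it through.** **1. Do the two rules agree?** The only figure available is the protocol's 4 h, described as twice the median tmax. Implied median = 4 / 2 = 2.0 h. No median tmax appears in the visible text of either document, so 4 h can be inverted but not reproduced independently.

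Window = 2 × median, with medians on the 0.5 h sampling grid of Protocol Table 8:

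| Median tmax (h) | SAP window (h) | Difference from 4 h |
|---|---|---|
| 1.5 | 3 | −1 |
| 2.0 | 4 | 0 |
| 2.5 | 5 | +1 |
| 3.0 | 6 | +2 |

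**2. A window below 4 h.** A subject withdrawn for emesis before 4 h is not a completer and leaves the PK set anyway. One who is not withdrawn meets the SAP 10.1 example of an unapplied withdrawal criterion. Little conflict arises.

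**3. A window above 4 h.** Protocol 5.5.2 decides whether participation continues, and does so at the investigator's discretion. SAP 10.2 decides whose data enter the primary model. A subject can complete the trial, count in the Safety Population and be left out of the PK set without either rule being broken.

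**4. Is the rule circular?** SAP 16.3.2 has parameters calculated and listed for all volunteers with sufficient concentration-time data, although the lead-in to its parameter table refers to the PK Analysis Set. Individual tmax values can therefore exist before membership is fixed. SAP 16.3.1 restricts reported summaries and analyses. No loop is forced.

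**5. Is dependence on assay results a fault?** The companion rule in SAP 10.2, predose above 5% of Cmax, also needs concentrations. Once its input is fixed, a mechanical rule leaves the analyst no discretion.

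**6. Size in power terms.** Inputs are the plan's fasted Cmax CV of 17.5%, ratio 0.95 and limits 0.80 to 1.25, with s = √ln(1 + 0.175²) = 0.174, SE = s√(2/n) and n − 2 degrees of freedom. Exact power for two one-sided tests is 88.2%, 91.3% and 93.6% at n = 18, 20 and 22, matching the plan's table. Removing one subject (treating the sequences as balanced) gives 91.3% to 89.8% from 20 to 19, and 96.6% to 96.0% from the planned 26 to 25.

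**The case for a change.** The strongest case for a change is that the SAP neither cites Protocol 5.5.2 nor repeats 4 h, and that it moves from one median for GIR to a median tied to a treatment. SAP 16.2 even speaks of fed and fasted treatments, so two or four medians are possible. The data review meeting may update definitions but sets no window, and the SAP does not say whether concentrations will be known by then. One sentence would settle it.

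A simulation gives this some weight. It takes two identical products, true median tmax 2.0 h, lognormal tmax with assumed CV 30–50% and assumed within-subject correlation 0–0.5, rounded to the sampling times. If each product's own sample median sets its window, then at n = 20 the two windows differ in 31–66% of trials, differ by at least 1 h in 11–37%, and at least one exceeds 4 h in 20–44%. At n = 12 the figures are 51–76%, 18–44% and 33–54%.

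Part of this stands: the source of the median is not stated. The simulation carries less. Neither document gives the CV or the correlation. At the planned 26 fasted subjects the figures are 21–57%, 8–32% and 14–37%; with a CV of 20% at n = 20 they fall to about 8%, 2–3% and 5%. A 6 h window arises in under 1% of trials at n = 20. With a prior median of 2.0 h for both products, every figure is zero. The results also count windows, not subjects: a window matters only if someone vomits inside the disputed hour or so.

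The complaint about SAP Section 9 is weak. Protocol 8.4 already excludes on comparability of PK results, and naming early emesis makes that condition specific more than it changes it. The added reference to events is a small documentation point.

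**Conclusion.** The concern does not hold as a reason to change the plan. The SAP and the protocol use the same multiple of the same quantity, and at the median the protocol implies, 2.0 h, they give the same window. A difference needs a median above 2.0 h that neither document states, together with a subject who vomits after 4 h and inside the longer window. Nothing here shows a wrong bioequivalence conclusion from following the rule as written.

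What is left is an unstated input. Analysts can take it from Protocol 5.5.2 or record it at the data review meeting before lock, and each vomiting case is to be discussed in the clinical study report, so any exclusion will be visible. Replacing the multiple with one fixed time would be a trade-off: it removes the ambiguity but gives up the link to each treatment's absorption time, and it would dictate the form of a clinical rule. If the sponsor did intend a median other than 2.0 h, the two passages would have to be reconciled by the sponsor and investigator; the documents do not indicate that.

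This rests on two assumptions: that the SAP's median is the one the protocol had in mind, and that emesis in the disputed interval is rare. The documents give no rate with which to test the second.
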